### 11.4 RELATIONSHIP OF AEs AND SAEs TO STUDY PROCEDURES

The investigator is obligated to assess the relationship between study mandated procedures and the occurrence of each AE/SAE. The investigator will use his/her clinical judgment to determine the degree of likelihood that the study design was responsible for the AE/SAE being reported. Alternative causes such as natural history of the underlying diseases (See Table 11.2 Sickle Cell Related Conditions), concomitant therapy, other risk factors, and the temporal relationship of the event to the study product will be considered and investigated. Table 11.2 serves as a guide to conditions typically associated with sickle cell disease, not an exclusionary list of conditions. If the investigator feels that one of the following conditions is related to the study procedures, he/she should report it as related.

**TABLE 11.2 Sickle Cell Related Conditions**

Expected AE	Expected AE	Expected AE
Acute chest syndrome	Development of autoantibodies associated with hemolysis	Pain, joint
Anemia	Development of clinically significant alloantibodies	Pain, long bone
Aplastic crisis	Elevated urinary urobilinogen	Pain, severe abdominal
Aplastic crisis/anemia	Fever	Priapism
Arthralgia	Hand-foot syndrome	Pulmonary embolism
Avascular necrosis of hip/shoulder	Hematuria	Pulmonary hypertension
Avascular necrosis of the femoral head	Hemiplegia	Pulmonary parenchymal infiltrates on chest x-ray
Bone infarction	Hemolysis	Pyelonephritis
Cardiomegaly	Hemolytic transfusion reaction	Renal failure
Cerebrovascular accident	Hepatosplenomegaly	Renal insufficiency/albuminuria
Cholecystitis, hepatic sequestration	Hyperplastic bone marrow	Renal papillary necrosis
Cranial nerve palsy	Hyposthenuria	Reticulocytosis ( $\geq 10\%$ – $20\%$ )
Decreased kidney function	Hypoxemia ( $PO_2 < 65\text{mmHg}$ )	Retinal disease
Decreased lung function	Infection, pneumococcal	Retinal hemorrhage
Delayed growth/puberty	Jaundice	Rhabdomyolysis
Depressed ESR	Leukocytosis	Sepsis
	Meningitis	Skin ulcers
		Splenic sequestration

### 11.5 TIME PERIOD, FREQUENCY, AND METHOD OF DETECTING AEs AND SAE

AEs and SAEs will be recorded for all subjects participating in the Phase II Pilot Transfusion study from randomization through the Exit Debriefing visit. At each visit, prior to transfusion or during the monthly call, an interval history recording hospitalizations, emergency room visits, and clinical events will be collected. Pre-transfusion measurements of hemoglobin (Hb) will be made, and ferritin will be measured at entry to the Pilot Transfusion Phase of the study if the ferritin lab data are more than three months old, at Month 3, as well as at the end of the study. During the course of the six-month transfusion period complications related to transfusions will be recorded, as will any observations of new endocrine or cardiac problems, specifically any new arrhythmia or cardiomyopathy.

Information to be collected includes the nature, date and time of onset, intensity, duration, causality, and outcome of the event. Even if the AE/SAE is assessed by the investigator as related to the subject's underlying sickle cell disease, its occurrence must be recorded in the source documents and on the appropriate page of the CRF.

### 11.6 RECORDING OF AEs AND SAEs

When an SAE occurs, the investigator is responsible for reviewing all documentation (e.g., hospital progress notes, laboratory test results, and diagnostic reports) relative to the event. The investigator or designee will then record all relevant information about an AE/SAE onto the appropriate page of the CRF and SAE Report Form, as applicable. It is

not acceptable for the investigator to send photocopies of the subject's medical records in lieu of completion of the appropriate CRF pages. Unless otherwise requested, transfer of subjects' medical records with the CRF should be restricted to hospital discharge summaries and autopsy reports, if available. When sending medical records, all subject identifiers (i.e., name, subject initials, and medical record number) must be obliterated prior to faxing the documents to the data coordinating center.

The investigator will attempt to establish a diagnosis of the event based on signs, symptoms, and/or other clinical information. In such cases, the diagnosis should be documented as the AE/SAE and not the individual signs/symptoms.

## 11.7 REPORTING

### 11.7.1 PROMPT REPORTING OF SAES (SITES TO THE SDMC)

The investigator or designee must report all SAEs to the data coordinating center by the end of the next business day after becoming aware of the event. The SAE Report Form will always be completed as thoroughly as possible, with all available details of the event, signed by the investigator (or sub-investigator), and forwarded to the appropriate project contact within the designated time frames. If the investigator does not have all information about an SAE, he/she will not wait to receive additional information before notifying the data coordinating center of the event. The following information is a minimum set of information required for all initial SAE reports:

- Investigator name
- Subject identifiers
- Adverse event term(s)
- Reason why the event is serious

Facsimile transmission of the SAE Report Form is the preferred method to transmit this information to the data coordinating center. Initial notification via the telephone does not replace the need for the investigator to complete and sign the SAE CRF within the time frames outlined in the protocol.

### 11.7.2 FOLLOW-UP OF AES AND SAES

After the initial AE/SAE report, the investigator is required to proactively follow each subject and provide further information on the subject's condition.

All AEs and SAEs documented at a previous visit/contact that are designated as ongoing will be reviewed at subsequent visits/contacts.

All AEs and SAEs will be followed until resolution (with or without sequelae), until the condition stabilizes, or until there is agreement between the investigator and the DSMB and/or NHLBI additional follow-up is not warranted.

New or updated information will be recorded on the originally completed SAE Report Form, with all changes initialed and dated. Once all updates have been made to the SAE report, the investigator must resign and date the report. The updated SAE CRF should be resent to the project contact for SAE receipt within the time frames outlined in the "Prompt Reporting of SAEs" section of the protocol.

### **11.7.3 REPORTING TO THE DATA AND SAFETY MONITORING BOARD (DSMB)**

Safety issues that arise in this study will be brought to the attention of the CSCC Data and Safety Monitoring Board (DSMB), which will make recommendations to the National Heart, Lung, and Blood Institute (NHLBI) regarding possible suspension of the study. The NHLBI will consider the DSMB's recommendations, determine an appropriate action and notify the Principal Investigator and the CSCC Statistics and Data Management Center (SDMC). The Principal Investigator will notify all participating investigators who will implement the actions directed by NHLBI.

All data from this study will be critically and carefully monitored by an independent DSMB to ensure the safety of study subjects as follows:

- All SAEs reported with SAE Criterion of Death will be reported to the DSMB within 15 calendar days of the SDMC Safety Specialist becoming aware of the event.
- On a quarterly basis, Rho will analyze SAE data and if it is determined that the data triggers a suspension guidelines as outlined in Table 11.3 "*Summary of Procedures and Timing for Alerting the DSMB and NHLBI Project Officer of Possible Serious Safety Issues*", the DSMB will perform a review of the information.
- On a semi-annual basis, the DSMB will receive statistical analyses and review of all safety reports to include AEs, SAEs, Transfusion Reactions and Clinical Laboratory Results.

## 11.8 SUSPENSION GUIDELINES

### 11.8.1 OVERVIEW

SAEs, AEs, and abnormal laboratory measures will be monitored quarterly throughout the study and if a significant imbalance between the two treatment groups in any of these measures is observed, the DSMB and NHLBI will be notified immediately to consider a suspension of enrollment into the study. This section details the process for assessing imbalances in these measures.

### 11.8.2 SERIOUS ADVERSE EVENTS

Three months after the first patient is enrolled in the study, and at the end of each three months thereafter, a quarterly statistical analyses and review of all SAEs will occur pending there have been SAEs reported during these timeframes. The SDMC will:

- Use the current version of the MedDRA dictionary to code all SAEs that have been recorded on study AE case report forms.
- Make a “snapshot” copy of the SAE data, including MedDRA codes.
- Create frequency tables of treatment x occurrence (yes or no, since inception of the study) of all patients. One table will be created for each highest level MedDRA term for which SAEs have been reported. The counting units are patients, not events.
- Compute Fisher’s Exact Test (FET) statistic to test the alternative hypothesis that occurrence of SAEs is not independent of treatment group. The FET p-value is not adjusted for multiplicity.
- If the FET p-value is less than the critical value shown in Table 11.3 and the active treatment group has a higher SAE rate, the SDMC will conduct further statistical analyses as indicated by the circumstances and report the results to the Chair of the DSMB subcommittee monitoring this study, the PI, and the NHLBI Project Officer.
- The SDMC will not file a report to the DSMB and the NHLBI Project Officer if the FET p-values is less than the critical value shown in Table 11.3.
- On a semi-annual basis the DSMB and the NHLBI Project Officer will receive a semi-annual report of all the SAEs reported regardless if a quarterly report was administered because a data trigger was found.

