### 11.8.6 PROCEDURES

This section specifies procedures for alerting the DSMB to serious safety issues that arise in this study. The incidences for alerting the DSMB are summarized in Table 11.3.

**TABLE 11.3 Summary of Procedures and Timing for Alerting the DSMB and NHLBI Project Officer of Possible Serious Safety Issues**

Situation or Event	Summary of Procedure (See text for details.)	Critical Value for DSMB “Alert”
SAEs reported with a SAE Criterion of Death	DSMB will be notified of all SAEs that are reported with a SAE criterion of Death within 15 days of the SDMC SAE Regulatory Specialist becoming aware of the event.	Death
SAEs (all)	1. SDMC performs quarterly analyses of MedDRA-coded SAEs, tabulates patients with SAEs classified by highest level MedDRA term. Report only when $p < \text{critical value}$ and active treatment group has higher AE rate. 2. SDMC performs semi-annual analyses of MedDRA-coded SAEs, tabulates patients with SAEs classified by highest level MedDRA term.	$p < 0.01$ $p$ not adjusted for multiplicity
AEs (all)	SDMC performs semi-annual analyses of MedDRA-coded AEs, tabulates patients with AEs classified by highest level MedDRA term. Report every six months. Alert only when FET $p < \text{critical value}$ and active treatment group has higher AE rate.	$p < 0.01$ $p$ not adjusted for multiplicity

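### The quarterly SAE alert is tested only within single MedDRA terms, so an excess spread over several terms is never tested as a whole

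*Protocol*

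**What the plan says.** Protocol section 11.8.1 announces that "if a significant imbalance between the two treatment groups in any of these measures is observed", the DSMB and NHLBI are to be told at once so that they can consider suspending enrollment.

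Section 11.8.2 gives the SAE procedure, run every three months on cumulative data:

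- **Tables.** "One table will be created for each highest level MedDRA term for which SAEs have been reported". "The counting units are patients, not events". No table across all terms is specified.
- **Test.** Fisher's exact test is used "to test the alternative hypothesis that occurrence of SAEs is not independent of treatment group", which is a two-sided alternative, with no multiplicity adjustment.
- **Trigger.** The coordinating center reports when the p-value is "less than the critical value shown in Table 11.3 and the active treatment group has a higher SAE rate". Table 11.3 sets the critical value at 0.01.
- **Conflicting bullet.** The next bullet says that no report goes to the DSMB and the NHLBI Project Officer when the p-value is below that same critical value.

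Outside this alert, deaths go to the DSMB within 15 days. All SAEs are reported semi-annually whether or not the trigger fired (11.8.2), as are the listed transfusion reactions (11.8.4).

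**The concern.** Apart from death notices, the quarterly test is the only scheduled route by which SAE data reach the DSMB between semi-annual reports. Section 14.4 lists transfusion risks of quite different kinds (allergies, fever, volume overload, infection, iron overload). Events of such kinds can be coded to different MedDRA terms. A harm that adds one or two patients to each of several terms can be substantial in total and still leave every per-term table far from significance. As written, nothing tests the total.

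The protocol also does not show how large an imbalance within one term has to be before the rule acts. A DSMB that hears nothing in a given quarter cannot tell how much that silence rules out.

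**Working it through.** The protocol states no operating characteristic for this alert, so there is no figure of its own to reproduce.

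**Inputs from the protocol**
- 36 patients randomized (7.1), half to each arm (9.4, 10.5): 18 per arm.
- Two-sided Fisher test, p < 0.01, transfusion arm higher (11.8.2, Table 11.3).

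**Assumption.** The protocol gives no SAE rates, so all true rates below are illustrative. Counts and rates are written transfusion v standard care.

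**Step 1: smallest firing counts in one table.** For equal arms of n and x v 0, the two-sided p is 2·C(n,x)/C(2n,x).

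| Arms | Outcome | Two-sided p | Alert |
|---|---|---|---|
| 18 v 18 | 6 v 0 | 2 × 18,564/1,947,792 = 0.0191 | no |
| 18 v 18 | 7 v 0 | 2 × 31,824/8,347,680 = 0.0076 | yes |
| 18 v 18 | 9 v 1 | 0.0072 | yes |
| 18 v 18 | 11 v 2 | 0.0045 | yes |
| 9 v 9 | 6 v 0 | 2 × 84/18,564 = 0.0090 | yes |
| 5 v 5 | 5 v 0 | 2 × 1/252 = 0.0079 | yes |
| 4 v 4 | 4 v 0 | 2 × 1/70 = 0.0286 | no |

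At 18 v 18, 8 v 1 (0.0178) and 10 v 2 (0.0116) do not fire. At 4 or fewer per arm no outcome can fire. With 17 transfused and 19 on standard care, 6 v 0 fires: p = 12,376/1,947,792 = 0.0064, because the opposite table (27,132/1,947,792 = 0.0139) is more probable and is left out of the sum.

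**Step 2: chance of an alert in one term.** This is the sum of binomial probabilities over all firing tables, for one look at 18 v 18:

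| True rates | Chance of alert |
|---|---|
| 20% v 5% | 2.2% |
| 30% v 10% | 6.2% |
| 60% v 30% | 13.9% |
| 40% v 10% | 19.3% |
| 30% v 0% | 27.8% |
| 40% v 0% | 62.6% |

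Simulated quarterly looks add little. For 30% v 5% the chance rises from about 13% to about 15–17%.

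**Step 3: an excess spread over four terms.** Assume 15% v 3% in each of four independent terms.
- Term by term: one table fires with probability 0.0070, so any of four fires with probability 1 − (1 − 0.0070)⁴ = 0.028, about 3%.
- Pooled: the any-SAE rates are 1 − 0.85⁴ = 0.478 and 1 − 0.97⁴ = 0.115. One table at these rates, same two-sided 0.01, fires with probability 0.302, about 30%.

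**Step 4: high background.** A pooled 70% v 50% fires with probability 0.044, about 4%.

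**Step 5: one-sided option.** One-sided p at 18 v 18 is 0.0095 for 6 v 0, 0.0089 for 8 v 1 and 0.0058 for 10 v 2, so the boundary falls by one patient. With equal true rates of 10–50%, the chance of a false alert per table and look is 0.02–0.20% two-sided and 0.10–0.57% one-sided.

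**The case against.** **Sidedness.** A reader might infer that testing two-sided while acting in one direction is an error, and that the rule fails to deliver its stated 1%. The document does not support that. A two-sided p-value with a direction condition is a complete, common rule, and the protocol never claims a one-sided 1% level. At 18 v 18 sidedness costs one patient on the boundary. The boundary comes mainly from the 0.01 threshold in a 36-patient trial.

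**An inert alert.** A reader might also infer that the alert can hardly ever fire, or never below 7 v 0. That goes too far. 7 v 0 holds at exactly 18 v 18. Smaller arms, or 17 v 19, fire at 6 v 0, and 5 per arm fires at 5 v 0. At 40% v 0% in one term the rule fires about 63% of the time. A trigger for considering suspension may reasonably be reserved for extreme imbalance.

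**Other oversight.** SAEs reach the coordinating center by the end of the next business day (11.7.1). Section 11.7.3 says, without reference to a p-value, that safety issues will be brought to the DSMB. Deaths and semi-annual reports are unaffected. What can be lost is up to about three months of earlier notice of a non-fatal imbalance. For AEs (11.8.3) nothing is lost, because an AE alert appears only in the semi-annual report.

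**Value of pooling.** The pooled table has the same 7 v 0 boundary, and its benefit depends on rates the protocol does not give. Hospitalization counts as an SAE (11.1.2) and Table 11.2 lists many expected sickle cell conditions, so background rates may be high and the gain small.

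All of this stands. It limits the point to the missing pooled table and the unstated boundary; it does not answer either of them.

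**Conclusion.** The gap is real and modest. An excess across terms is never tested as a whole, which falls short of what 11.8.1 promises. Under the assumed 15% v 3% in each of four independent terms, one pooled table raises the chance of an alert from about 3% to about 30% at the same threshold. If events cluster in the same patients, or if background SAE rates are high, the gain is smaller (about 4% at a pooled 70% v 50%). The counts needed within one term follow from the arithmetic of 18 per arm and 0.01 and need no rate assumption, apart from their dependence on the exact arm sizes at each look.

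The consequence is limited to early warning of non-fatal SAE imbalances between semi-annual reports. It is a cheap improvement to a stated rule and does not show that DSMB oversight fails.

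Separately, the two bullets in 11.8.2 on reporting when the p-value is below the critical value cannot both apply and must be reconciled.

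**What to change.** 1. In 11.8.2 and in both printings of Table 11.3 (11.8.6 and 11.9.1), add one table of patients with any SAE to the per-term tables, under the same trigger.
2. Print the smallest firing counts in Table 11.3, for example 7 v 0, 9 v 1 and 11 v 2 at 18 v 18, 6 v 0 at 9 per arm, and none at 4 or fewer per arm. State that they shift with arm sizes.
3. Reconcile the two conflicting bullets in 11.8.2.
4. Optionally, since the alert acts in one direction only, use the one-sided Fisher p-value against 0.01. The 18 v 18 boundary becomes 6 v 0, and the printed counts change accordingly.

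The cost is one more table per review and a slightly higher chance of a false alert. With equal true rates of 10–50%, that chance stays at or below about 0.2% per table and look two-sided, or about 0.6% one-sided. It accumulates over terms and looks, but an alert only prompts review. The AE rule in 11.8.3 can stay as it is, because changing its test would move no reporting date.

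### Section 11.8.2 both requires and forbids the quarterly SAE report when the Fisher test crosses its threshold, and the AE and laboratory review frequency is stated two ways

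*Protocol*

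**What the plan says.** **SAE signal rule.** Section 11.8.2 has the SDMC tabulate patients with SAEs by arm every three months, one table per highest-level MedDRA term, and apply Fisher's exact test (FET). The fifth bullet sets the trigger: "If the FET p-value is less than the critical value shown in Table 11.3 and the active treatment group has a higher SAE rate". Further analysis must then follow, and the center is to "report the results to the Chair of the DSMB subcommittee monitoring this study, the PI, and the NHLBI Project Officer". By contrast, the sixth bullet says that this center "will not file a report to the DSMB and the NHLBI Project Officer if the FET p-values is less than the critical value". The critical value meant is again the one in Table 11.3. The seventh bullet promises a semi-annual report of all SAEs, whether or not a quarterly trigger occurred.

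**Table 11.3.** It is printed in 11.8.6 and again in 11.9.1. Both copies set the SAE threshold at p < 0.01, unadjusted, and confine the quarterly report to results below it where the "active treatment group has higher AE rate".

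**Review frequency.** Section 11.8.1 says that "SAEs, AEs, and abnormal laboratory measures will be monitored quarterly throughout the study", with immediate notice to the DSMB and NHLBI of a significant imbalance. Sections 11.8.3 (AEs) and 11.8.5 (laboratory results) schedule these reviews every six months.

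**The concern.** The fifth and sixth bullets of 11.8.2 share the same p-value condition and lead to opposite actions. When p is below 0.01 and the transfusion arm is worse, the SDMC cannot obey both.

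The quarterly SAE test is the only statistical comparison of the arms designed to reach the DSMB between semi-annual reports. AE alerts, transfusion reactions and laboratory results all go into semi-annual reports. If the sixth bullet were followed, that between-report route would be closed in exactly the case it exists for.

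The frequency conflict is a second, smaller problem of the same kind. The overview promises quarterly monitoring and immediate notice for AEs and laboratory measures, and the detailed sections do not provide it.

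**Working it through.** The protocol states no figure to reproduce here. The check is a comparison of passages, with a count to show where the bullets collide.

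**1. What each place says when p < 0.01 and the transfusion arm is worse**

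| Protocol section | Quarterly SAE report? |
|---|---|
| 11.7.3 | Yes: a triggered guideline leads to DSMB review |
| 11.8.1 | Yes: immediate notice of a significant imbalance |
| 11.8.2, fifth bullet | Yes |
| 11.8.2, sixth bullet | **No** |
| 11.8.2, seventh bullet | Presupposes that triggered quarterly reports exist |
| Table 11.3 in 11.8.6 | Yes |
| Table 11.3 in 11.9.1 | Yes, quarterly when the threshold is met |

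The sixth bullet stands alone. Inserting a *not* before the comparison would bring it into line on the p-value. It would still lack the direction condition that the fifth bullet and Table 11.3 carry.

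**2. How the bullets divide the possible results (illustration)**

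Inputs: 36 randomized in two equal groups (13.1 and 9.4), so 36 / 2 = 18 per arm; two-sided Fisher test, because 11.8.2 tests a non-directional alternative; threshold 0.01. With 0 to 18 affected patients in each arm, one MedDRA term has 19 × 19 = 361 possible tables.

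| Result | Tables | Fifth bullet and Table 11.3 | Sixth bullet |
|---|---|---|---|
| p < 0.01, transfusion arm higher | 61 | report | no report |
| p < 0.01, standard care arm higher | 61 | no quarterly report | no report |
| p ≥ 0.01 | 361 − 61 − 61 = 239 | no quarterly report | silent |

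The sixth bullet therefore opposes the rule in every triggering table and says nothing about the 239 it presumably meant to cover. With the corrected wording, 61 tables lead to a report and 239 + 61 = 300 do not, which matches Table 11.3. With the 15 completers per arm, 38 of 16 × 16 = 256 tables trigger, and the pattern is the same. These are counts of possible tables, not probabilities.

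The smallest triggering result with no affected standard care patient is 7 of 18 versus 0 of 18 (p = 0.0076); 6 versus 0 gives p = 0.019. The disputed instruction therefore applies to large imbalances.

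**3. Length of the delay**

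SAE looks fall at months 3, 6, 9, 12 and so on after first enrollment. Section 11.8.3 starts the AE semi-annual cycle at month 6. If the semi-annual SAE report follows the same cycle, a signal found at month 3 or 9 waits 6 − 3 = 3 months, and one found at month 6 or 12 waits essentially not at all. Section 11.8.2 does not tie the two schedules together. If they were offset, the wait could be longer, but it is limited by the six-month interval between reports.

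**4. Review frequency**

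| Data | 11.8.1 | Detailed sections and Table 11.3 |
|---|---|---|
| SAEs | quarterly | quarterly test (11.8.2): consistent |
| AEs | quarterly, immediate notice | semi-annual; alert carried in the semi-annual report (11.8.3) |
| Laboratory | quarterly, immediate notice | semi-annual (11.8.5) |

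Section 11.7.3 also lists AEs and laboratory results as semi-annual. The conflict is confined to these two rows.

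**The case against.** The strongest reply is that nobody would be misled. The intended rule appears in the bullet just before, in 11.7.3, in 11.8.1 and in both copies of Table 11.3, and the likeliest cause is a dropped word. Other safeguards remain: sites report every SAE to the data coordinating center by the end of the next business day, deaths reach the DSMB within 15 calendar days, and all SAEs are reported semi-annually regardless of the trigger. This is right about intent and about the limits of the harm. It does not remove the contradiction from the text that the SDMC is meant to carry out.

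Two stronger readings are tempting, and the protocol supports neither.

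- A reader might infer that the SAE rule as a whole is inverted, so that a triggering excess is never escalated early. The protocol both requires and forbids the report. One sentence is reversed, and every other statement of the rule points the other way.
- A reader might infer that the trigger is too insensitive and should become, for example, a one-sided p < 0.05 rule with an added row for any SAE. The unadjusted p < 0.01 threshold with a direction condition is stated consistently and is a defensible choice for repeated looks across several MedDRA terms. The protocol claims no detection probability for it. Showing it to be weak requires assumed event rates that the protocol does not give. The one-sided 0.05 comparison also changes sidedness and alpha together: for assumed true rates of 30% versus 5% at 18 per arm, the alert probability is 13% under the stated rule, 24% with one-sided 0.01 and 47% with one-sided 0.05. This is a design preference, not an error in the document.

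**Conclusion.** The contradiction in 11.8.2 is real and sits in a safety decision rule. The sixth bullet is the reversed one, and it also omits the direction condition. If it were followed, a triggered quarterly SAE signal would be held until the next semi-annual report, up to about 3 months later, or half of one patient's six-month treatment period (3 / 6). The 3 months assumes that the semi-annual SAE report coincides with every second quarterly look. The harm is a delayed alert, with no loss of SAE data: death notifications and semi-annual SAE reporting are untouched.

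The frequency conflict between 11.8.1 and 11.8.3, 11.8.5 and Table 11.3 is also real, and is limited to AEs and laboratory measures. Neither conclusion depends on an assumed event rate.

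**What to change.** 1. **Section 11.8.2, sixth bullet.** Reword it to say that the SDMC files no quarterly SAE report if the Fisher p-value is *not* below the Table 11.3 critical value, *or* if the active treatment group does not have the higher SAE rate. This makes it the exact complement of the fifth bullet and matches Table 11.3.
2. **Review frequency.** Reconcile 11.8.1 with 11.8.3, 11.8.5 and Table 11.3 so that one frequency, and one timing of notification, is stated for AEs and for laboratory results.

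The cost is a short protocol correction and a memo to the SDMC. It needs no new data, visits or patients, and no change to the test or its threshold. It should be in place before the next quarterly SAE analysis.
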